4.2.2. Safety

To investigate the safety of LY3209590 compared with insulin degludec for the following endpoints:

1. Incidence and rate of hypoglycemia events during the treatment period
2. Incidence of treatment-emergent serious adverse events (TE-SAEs)

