5.10.3.2. Hypoglycemia Events

According to 2020 American Diabetes Association standard of medical care in diabetes, there are two levels of hypoglycemia defined by glucose concentration:

- Level 1: glucose < 70 mg/dL (3.9 mmol/L) and glucose ≥ 54 mg/dL (3.0 mmol/L)
- Level 2: glucose < 54 mg/dL (3.0 mmol/L)

With the above glucose reading requirement for Level 1 and 2 hypoglycemia, the following type of hypoglycemia events will be derived: documented hypoglycemia, documented nocturnal hypoglycemia (occurs between bedtime and waking), and documented non-nocturnal hypoglycemia (occurs between waking and bedtime).

Per the study protocol, severe hypoglycemia is reported as a serious AE. Severe hypoglycemia is defined in the protocol and is consistent with the ADA definition, but also requires investigator confirmation of neurological impairment. The 2020 American Diabetes Association standard of medical care in diabetes also classified severe hypoglycemia as Level 3 hypoglycemia. During a severe hypoglycemia episode, the participant has an altered mental status and cannot assist in his/her own care, may be semiconscious or unconscious, or experience coma with or without seizures, and may require assistance of another person to actively administer carbohydrate, glucagon, or other resuscitative actions. This information will be collected in the patient eDiary and the severe hypoglycemia will be analyzed.

Table BDCP.1 provides the summary of statistical method for hypoglycemia event related analysis. Additionally, severe hypoglycemia events will be listed, and incidence of severe hypoglycemia will be compared between treatments using Fishers' exact test. The Level 2 and Level 3 are usually considered as clinically significant hypoglycemia. Therefore, the analysis on a composite of Level 2 and Level 3 (denoted as Level 2/3) hypoglycemia will also be conducted.

Table BDCP.1. Hypoglycemia Event Related Analyses

Endpoint	Time Point*	Statistical Method
Rate of hypoglycemia events for Level 1 and Level 2/3 
 • Documented • Nocturnal • Non-Nocturnal 	0-12, 0-26, 12-26 weeks, post-treatment period (up to Visit 801)*	Negative binomial regression with treatment, baseline HbA1c, baseline hypoglycemia incidence for the same type of the dependent variable, log (exposure in year) as the offset in the model.

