Incidence of hypoglycemia events for Level 1 and Level 2/3 
 • Documented • Nocturnal • Non-Nocturnal 	0-12, 0-26, 12-26 weeks, post-treatment period (up to Visit 801)*	Logistic regression with treatment, baseline HbA1c, baseline hypoglycemia incidence for the same type of the dependent variable in the model.

 • Proportion of patients with HbA1c <7% without documented nocturnal hypoglycemia event (Level 1 and Level 2) • Proportion of patients with HbA1c $\leq 6.5\%$ without documented nocturnal hypoglycemia event (Level 1 and Level 2) 	0-26 weeks	Logistic regression with treatment, country, baseline HbA1c, and baseline nocturnal hypoglycemia incidence in the model.

Abbreviations: HbA1c = hemoglobin A1c; Level 2/3 = Level 2 and Level 3 composite.

Note: The hypoglycemia rate per year during defined period is calculated by the number of hypoglycemia within the period/number of days patient at risk within the period*365.25 days. The hypoglycemia incidence during defined period indicates if the patient has at least 1 hypoglycemia events within the period (Yes/No). The baseline hypoglycemia rate is the rate calculated between Visit 2 and Visit 3.

*Analyses for endpoint during post-treatment period (up to Visit 801) will include all of the data after study drug discontinuation on Safety population; analyses for endpoints during other time points will include all data before study drug discontinuation on Safety population.

The following is the example of the SAS code of the negative binomial regression for analyzing the rate of hypoglycemia events.

```

proc glimmix empirical data=DATA;
  class TREATMENT;
  model HYPO_FREQ=TREATMENT [BASELINE_HYPO]
    /dist=nb link=log offset=log(exposure in
    days/365.25);
    lsmeans TREATMENT/OM pdiff cl alpha=0.1 ilink;
    random _residual_;
run;

```

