5.11.2. CGM Variables and Analysis

The continuous variables derived from CGM will be summarized and compared between treatment groups by visit using MMRM model. The model will include the treatment, HbA1c stratum (<8.5% or >=8.5%), baseline value of the dependent variable, visit, and treatment by

visit interaction. The raw mean and LS mean difference between treatment groups will be summarized.

For the between-day and within-day glucose variability, the variable will take log-transformation before performing the MMRM analysis.

The binary variables will be analyzed using a longitudinal logistic regression. In the longitudinal logistic regression model, the independent variables of treatment, baseline HbA1c value, baseline continuous variable corresponding to the binary dependent variable, visit, and treatment by visit interaction will be used.

For the hypoglycemia episodes defined by CGM, the analysis using a negative binomial model with the offset of log (exposure in year) will be performed. The model will include treatment, baseline HbA1c, baseline incidence for the dependent variable.

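### The negative binomial hypoglycemia models adjust for a Yes/No baseline indicator and leave the defined baseline rate unused; using the log rate would gain precision for frequent events at almost no cost

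*SAP*

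**What the plan says.** SAP 4.2.2 lists as a secondary safety endpoint: "Incidence and rate of hypoglycemia events during the treatment period".

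For event rates, SAP Table BDCP.1 specifies "Negative binomial regression with treatment, baseline HbA1c, baseline hypoglycemia incidence for the same type of the dependent variable", with log exposure as offset. For incidence it specifies "Logistic regression with treatment, baseline HbA1c, baseline hypoglycemia incidence for the same type of the dependent variable in the model". The table note defines incidence: "The hypoglycemia incidence during defined period indicates if the patient has at least 1 hypoglycemia events within the period (Yes/No"). It then adds: "The baseline hypoglycemia rate is the rate calculated between Visit 2 and Visit 3". That is the only baseline quantity in the note with a stated window, and no listed model takes it as a covariate.

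For CGM-defined episodes, SAP 5.11.2 again uses a negative binomial model: "The model will include treatment, baseline HbA1c, baseline incidence for the dependent variable".

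The SAS example after the table shows only a bracketed placeholder, BASELINE_HYPO, so the code does not settle whether incidence or rate is meant. It also omits the baseline HbA1c that the table lists.

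**The concern.** A count outcome is being adjusted for a baseline count reduced to two levels. Where events are frequent, most participants score Yes and the indicator separates them poorly. The indicator also ignores time at risk: by the protocol's Schedule of Activities, Visit 2 falls at Week -1 with a window of 3 days either side, so the baseline period runs from about 4 to 10 days.

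The SAP keeps the baseline continuous elsewhere. The HbA1c model (5.7) and the continuous CGM models (5.11.2) use the baseline value, and the binary CGM outcomes are adjusted for the underlying continuous baseline. No reason is given for treating hypoglycemia rates differently.

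At stake is the width of the interval for the rate ratio. The protocol names hypoglycemia as the potential downside of a weekly insulin (2.2), and the trial is sized for HbA1c alone (9.2).

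**Working it through.** **The plan's own figure.** The only sizing is for HbA1c: n per arm = 2 × 1.1² × (1.645 + 0.842)² / 0.4² = 93.5, so 94 against 95 stated. Power with 95 per arm is 0.805, and 190 / 0.8 = 237.5, so 238. It reproduces, but there is no corresponding figure for hypoglycemia.

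**Inputs from the documents.** 119 per arm (protocol 9.2); 26 weeks of treatment (protocol 4.1), taken as 0.5 years; a baseline of 4 to 10 days (protocol 1.3); 2-sided alpha 0.1 (SAP 5.1); sandwich standard errors, as the SAS example requests the empirical option.

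**Assumptions, because the documents are silent.** Log-normal patient rates averaging 3 to 260 events per patient-year; variance of the between-patient rate multiplier 0.6 to 1.2; correlation of baseline and on-treatment log rates 0.5 to 0.8, with 1.0 as an extreme. Baseline HbA1c was left out of the simulated models.

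**Step 1: how much the baseline period holds.** Expected events in a nominal week = rate × 7 / 365.25. At 10 per year this is 0.19; at 100 it is 1.92.

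**Step 2: rate models.** Negative binomial models were fitted with the Yes/No covariate and with log((events + 0.5)/days). Gain in equivalent sample size = 1/(SE ratio)² − 1. For example, at 100 per year, variance 1.2 and correlation 0.8, the SEs are 0.105 and 0.121: the ratio is 0.868 and the gain 32.8%. Gains below combine runs that used sandwich SEs with runs that used the empirical variance of the estimate across simulated trials.

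| Events per patient-year | Expected in 7 days | Share Yes | SE ratio, log rate / Yes-No (correlation 0.5-1.0) | Gain (correlation 0.5-0.8) |
|---|---|---|---|---|
| 3 | 0.06 | about 5% | 0.99-1.01 | about 0 |
| 10 | 0.19 | about 16% | 0.99-1.01 | about 0 |
| 30 | 0.57 | about 36% | 0.92-0.99 | roughly 1-6% |
| 60 | 1.15 | 54-59% | 0.83-0.98 | 4-27% |
| 100 | 1.92 | 67-73% | 0.73-0.96 | 8-35% |
| 260 | 4.98 | about 90% | not tabulated | 17-82% |

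At 3 to 10 per year the empirical-variance results ran from −3% to +2%; changes that small are best read as zero. At 30 per year one setting (variance 1.2, correlation 0.8) gave 10.3%, above the range shown. A correlation of 1.0 with variance 1.2 gives 47% at 60 and 89% at 100 per year, but that requires patients' relative rates to survive the switch and titration unchanged.

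**Step 3: incidence models.** Logistic fits used an assumed rate ratio of 0.6, rates of 1 to 30 per year and 600 trials per setting. Power was 0.782 with either covariate at 3 per year (variance 0.6, correlation 0.8). The largest differences were 1.2 points and went both ways: 0.795 against 0.807, and 0.725 against 0.713. Some fits failed, mainly with the Yes/No covariate at 1 per year (554 to 565 of 600 usable) and with both covariates at 30 per year, where 97-99% had an event. No gain was detectable.

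**The case against.** The strongest reply is that this is a preference between two valid analyses. Hypoglycemia carries no margin, power or success rule, and the size of the gain depends on three quantities that the documents do not give. For rare types the gain is nil. All of that stands.

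A second reply is that the log rate brings its own noise. Among participants with no baseline events, a 4-day and a 10-day lead-in differ by ln(10/4) = 0.92 through scheduling alone, close to the step from zero to one event, ln(1.5/0.5) = 1.10, and the 0.5 is arbitrary. The mechanism is real, but the simulations varied the window over 4 to 10 days and showed no material loss even at 3 to 10 events per year.

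Third, continuous CGM measures such as time below 70 and 54 mg/dL already have continuous baseline adjustment. They are different endpoints, and this does nothing for the event-rate models.

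A reader might also infer that nearly every participant has a baseline event, leaving the indicator almost constant. The documents do not support that. They give no rate; Table BDCP.1 has its own models, separate from the sensor-defined episodes of SAP 5.11.3.2, and hypoglycemic events are entered by patients in the diary (protocol 10.1.6); and the covariate is specific to event type, so it can be informative for rarer ones. The protocol also excludes people with severe hypoglycemia or unawareness in the previous 6 months.

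**Conclusion.** The point holds for the negative binomial rate models only, as a precision improvement. For correlations of 0.5 to 0.8 the gain is about zero up to 10 events per patient-year, roughly 1-6% at 30, 4-27% at 60 and 8-35% at 100. In interval width, 8% is 1 − 1/√1.08 = 4% narrower and 35% is 1 − 1/√1.35 = 14% narrower. At 260 per year the gain is 17-82%; CGM-defined episodes would benefit to that degree only if they are that frequent, which the documents do not say.

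Three stronger readings should be resisted. The planned covariate does not bias the comparison, since it is measured before randomization. The incidence models need no change, since none of the simulated settings showed a detectable gain. And the endpoint is secondary, not labelled key, so no primary conclusion depends on this.

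**What to change.** In the rate rows of Table BDCP.1 and in the CGM episode model of SAP 5.11.2, replace baseline incidence with log((events + 0.5)/days at risk) between Visit 2 and Visit 3, for the same event type as the outcome. For CGM episodes, count them over the baseline CGM data. Define BASELINE_HYPO in the SAS example as that variable and add the baseline HbA1c that the table lists. The subgroup rate models in SAP 5.12 borrow the same fixed effects and would follow. Leave the logistic incidence models as they are, but state that their baseline incidence is also taken between Visit 2 and Visit 3.

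The cost is one covariate definition and a few lines of code, using data already collected. Because the study team knows the treatment assignments (SAP section 6), the change should be fixed in a dated SAP revision before database lock and before any rate model is fitted by arm.

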Pharmacokinetics 
 To characterize the PK of LY3209590 in study participants with T1DM 	
 LY3209590 population-based parameters, such as AUC within dosing interval at Weeks 12 and 26
Tertiary/Exploratory	

 To establish the equivalent dose of LY3209590 relative to insulin degludec To investigate the safety and tolerability of LY3209590 compared with insulin degludec in study participants with T1DM 	
 Insulin dose at baseline and Week 26 Treatment-emergent AEs Incidence and rate of hypoglycemia events during the post-treatment follow-up period Discontinuation of IP due to AEs Clinical laboratory results Systematic assessment of injection site reactions Insulin dose for prandial as well as basal insulin during treatment period and follow-up period Incidence and rate of hypoglycemia during treatment and follow-up period

Objectives	Endpoints
	
 • Incidence and rate of daytime hypoglycemia • Liver aminotransferase change from baseline to Weeks 12 and 26 • Triglyceride and FFA change from baseline to Weeks 12 and 26 • Body weight change from baseline to Weeks 12 and 26

 • To explore quality of glycemic control compared with insulin degludec using CGM 	
 • Glucose time in target range, time in hyperglycemia, time in hypoglycemia • Duration of hypoglycemic events

 • To establish the relationships between dose/exposure and key safety and efficacy measures for LY3209590 	
 • LY3209590 exposure-response relationships for key efficacy and safety measures (e.g., glycemic control, hypoglycemia and safety labs).

 • To characterize the effects of LY3209590 on exploratory PD biomarkers • To explore the development of LY3209590 ADAs • To explore the compliance with the dosing regimen 	
 • Lipids (cholesterol, LDL, HDL, triglycerides) • 6-point SMBG glucose profiles • Biomarkers of lipolysis (FFA) • The frequency of antibody formation to LY3209590 and relationship to safety and efficacy markers will be determined • Incidence and percentage of missed doses of LY3209590 and insulin degludec.

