4.1. Overall Design

Study I8H-MC-BDCP (BDCP) is a multicenter, randomized, open-label, parallel, comparator-controlled Phase 2 study with 3 study periods. The study is designed to evaluate the efficacy and safety of LY3209590 compared with insulin degludec in patients with T1DM treated with MDI for at least 3 months prior to screening.

The study will consist of 3 periods:

- Study Period 1: screening and lead-in period, approximately 2 weeks
- Study Period 2: treatment period, 26 weeks
- Study Period 3: safety follow-up period, 5 weeks

The study schema is presented in Section 1.2.

Study governance considerations are described in detail in Section 10.1.

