All randomized participants should have a comprehensive efficacy and safety evaluation approximately 1 week after the last dose of LY3209590 and 1 day after the last dose of insulin degludec, and a safety follow-up visit approximately 6 weeks after the last dose of LY3209590 and 5 weeks after the last dose of insulin degludec. During the safety follow-up study period, participants will continue CGM and will be switched back to their previously used basal insulin therapy if appropriate (see Section 6.7.1). Participants will also be required to return any remaining used or unused IP at Visit 20 and the eDiary at Visit 801 to the investigative site.

Participants who *complete the treatment period* will have a comprehensive End-of-Treatment efficacy and safety assessment (Week 26; Visit 20) approximately 1 week after the last dose of

LY3209590 and 1 day after last dose of insulin degludec and a safety follow-up assessment (Visit 801) approximately 6 weeks after the last dose of LY3209590 and 5 weeks after the last dose of insulin degludec.

Participants who *discontinue IP prior to completion* of the treatment period for any reason should follow the visit schedule off study drug and also have a comprehensive End-of-Treatment efficacy and safety assessment (ED 1) approximately 1 week after the last dose of LY3209590 and 1 day after the last dose of insulin degludec or as soon as reasonably possible thereafter, and should have a safety follow-up assessment (ED 2) approximately 6 weeks after the last dose of LY3209590 and 5 weeks after the last dose of insulin degludec. Study activities at Visits ED 1 and ED 2 are identical to Week 26 (Visit 20) and Visit 801, respectively. This close follow-up is necessary since LY3209590 has a **CCI** and the switch to an alternative, commercially available insulin must be closely monitored to prevent hypoglycemia due to an accumulation of insulin action.

Participants who discontinue IP prior to the completion of the treatment period will be encouraged to remain in the study and to complete any scheduled study procedures that occur until Visit 20. Participants remaining in the study will receive an appropriate glucose-lowering regimen.

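### Post-treatment hypoglycemia incidence is counted over unequal follow-up: about 5 weeks for completers, up to about 26 weeks or more for early discontinuers who stay in the study

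*SAP*

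**What the plan says.** The protocol (Section 3) lists among its tertiary/exploratory endpoints "Incidence and rate of hypoglycemia events during the post-treatment follow-up period". Section 4.1 gives the length of that period: "Study Period 3: safety follow-up period, 5 weeks". For completers it runs from Visit 20 (Week 26) to Visit 801 (Week 31). For participants who stop study drug early, the Schedule of Activities has a matching pair of visits, ED1 and ED2, with ED2 five weeks after ED1.

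The SAP (5.10.3.2, Table BDCP.1 footnote) does not use that period to close the window. The post-treatment analysis "will include all of the data after study drug discontinuation on Safety population", and the table labels the period as running up to Visit 801. Under Protocol 4.1.1, participants who stop study drug early "will be encouraged to remain in the study and to complete any scheduled study procedures that occur until Visit 20". Protocol 8.3.7.1 has hypoglycemia collected until the last study visit.

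Incidence in Table BDCP.1 is whether a participant had at least one event in the period. Its model is "Logistic regression with treatment, baseline HbA1c, baseline hypoglycemia incidence for the same type of the dependent variable in the model". The rate is "number of hypoglycemia within the period/number of days patient at risk within the period*365.25 days", modelled by negative binomial regression with "log (exposure in year) as the offset in the model".

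**The concern.** A yes/no outcome depends on how long each participant is watched. Under the footnote, that length depends on when the participant stopped study drug and whether they stayed in the study, and the incidence model has nothing to account for it. If one arm has more participants who stop drug and stay, its post-treatment incidence is higher even when the underlying risk is the same in both arms.

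Hypoglycemia is an adverse event of special interest here. The protocol calls for close follow-up after LY3209590 is stopped because insulin action may overlap (Sections 4.1.1 and 6.7.1). A post-treatment comparison that partly reflects discontinuation patterns would not answer that question cleanly.

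**Working it through.** **Planned windows.** The plan's own figure reproduces: 2 + 26 + 5 = 33 weeks of maximum participation (Protocol 1.1). For LY3209590 completers, the last dose is at Week 25 (Protocol 6.7.1). Adding the 7 days in SAP 5.10.1 gives Week 26, and 31 − 26 = 5 weeks. For degludec, Week 26 to Week 31 is also 5 weeks.

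**Windows for early discontinuers who stay.** Someone who stops after the first dose contributes 26 − 1 = 25 weeks (LY3209590) or about 26 weeks (degludec) to Visit 20. If Visit 801 is also done, these become 30 and 31. The Schedule of Activities does not settle whether such participants attend Visit 801: its footnote gives Visit 801 to those who complete Visit 20, and ED1/ED2 to those who stop drug but remain. Both cases are therefore shown.

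**Assumptions not in the documents.** End of treatment t is uniform over 0 to 26 weeks in discontinuers, all of whom stay. Event rates are 0.5 to 50 per year, constant over time and equal in both arms. Negative binomial dispersion is 0 (Poisson) or 1. Retained discontinuers make up 5%, 10% or 20% of an arm.

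**Mean follow-up of a retained discontinuer.** To Visit 20 with a minimum of 5 weeks, L = max(5, 26 − t). The mean is (21 × 15.5 + 5 × 5)/26 = 13.5 weeks. To Visit 801, the mean of 31 − t is 18.0 weeks.

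**Incidence at 5 events/year (Poisson).** The formula is 1 − exp(−rate × weeks/52.18).
- 5 weeks: 1 − exp(−0.479) = 38.1%.
- 18 weeks (stopped at Week 8, followed to Visit 20): 1 − exp(−1.725) = 82.2%.
- Averaged over uniform stopping times, to Visit 20: 66.6%.
- Arm with 5% retained discontinuers: 0.95 × 38.1 + 0.05 × 66.6 = 39.5%.
- Arm with 20%: 0.80 × 38.1 + 0.20 × 66.6 = 43.8%.

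The true difference is zero in this example.

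**Spurious odds ratio over all assumed rates and both dispersions.**

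| Retained discontinuers | To Visit 20 | To Visit 801 |
|---|---|---|
| 20% vs 10% | 1.06–1.14 | 1.08–1.20 |
| 20% vs 5% | 1.09–1.23 | 1.13–1.34 |

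At 50 events/year (Poisson, to Visit 20), arm incidence is 99.2% at 5% and 99.3% at 20%. The odds ratio is still 1.14, but only about one participant in 119 is event-free, so it could hardly be estimated. With a common 5-week window the ratio is 1.00 throughout.

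**Rate.** Let k be the rate after week 5 divided by the rate in the first 5 weeks, and d the share of retained discontinuers. The person-time rate relative to the early rate is [5(1 − d) + d(5 + k(L − 5))]/[5(1 − d) + dL]. With d = 0.20 and L = 13.48, the denominator is 4 + 2.696 = 6.696, so retained discontinuers supply 2.696/6.696 = 40% of person-time.
- k = 0.5: 5.848/6.696 = 0.87.
- k = 1: 1.00.
- k = 2: 8.392/6.696 = 1.25.

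Giving each participant equal weight instead, the values are 0.95, 1.00 and 1.10.

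**The case against.** A reader might go further and infer that the open window dilutes the washout rate, so that incidence and rate are pushed in opposite directions. The documents do not support that. The rate uses days at risk and an exposure offset, so unequal follow-up alone leaves it unbiased. A shift needs risk that changes with time since stopping, and the calculation shows it can go either way. Protocol 4.1.1 and 6.7.1 give overlapping insulin action as a reason for monitoring and cautious transition, but they give no early or late event rates.

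A reader might also infer that the arm with more discontinuations is the one affected. What matters is discontinuers who stay. Those unwilling to return have the early termination visit as their last (Protocol 4.1.1) and add little or no post-treatment time. The 20% planning figure in Protocol 9.2 is dropout, not stopping drug while remaining in the study, and it is not split by arm.

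On size, 20% versus 5% is a fourfold imbalance. The resulting 4.3 points compare with a standard error of √[(0.438 × 0.562 + 0.395 × 0.605)/119] = 6.4 points at about 119 per arm. At 20% versus 10% the gap is 43.8 − 40.9 = 2.9 points.

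The all-data rule also follows the SAP's general safety approach, and SAP 5.10.1 summarizes follow-up duration by arm, which would reveal an imbalance. Finally, LY3209590 washout may take up to 10 weeks (Protocol 6.7.1), so a 5-week cut removes some washout time in retained discontinuers.

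All of this limits the point, but it does not rescue the incidence analysis. A table of follow-up duration shows the imbalance without correcting for it, and noise of similar size is no reason to keep an avoidable bias.

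**Conclusion.** The point holds for incidence. As written, the window is open-ended, the model has no time term, and the comparison is biased whenever the share of retained discontinuers differs by arm. The bias is modest: 4.3 points in the worked example, with spurious odds ratios of about 1.06 to 1.34 over the assumed range. In percentage points it is close to nothing for event types that nearly everyone has. All of these sizes rest on assumed event rates, stopping times and retention.

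For the rate, the finding is only that the all-data figure describes a different period from the protocol's 5 weeks, and that it may shift either way if risk changes over time. The endpoint is exploratory. The primary HbA1c analysis and the secondary treatment-period hypoglycemia analysis are unaffected.

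**What to change.** In the Table BDCP.1 footnote, define one post-treatment window for every participant. It starts at end of treatment as in SAP 5.10.1 (last dose date for degludec, last dose date + 7 days for LY3209590) and ends at the earlier of 35 days later or last contact. This matches Visit 801 and ED2. Use it for incidence, and for the main rate analysis so that both describe the same period. Keep the all-data, exposure-adjusted rate as a supportive analysis, and report later off-drug events separately.

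State in the SAP that 5 weeks is the longest window planned for all participants but does not cover a washout of up to 10 weeks. The cap also does not lengthen the short follow-up of those who leave early, so follow-up time within the window should be shown by arm.

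The cost is SAP wording and one date cut-off, with no new data. Events after day 35 leave the main post-treatment analysis but stay in the supportive rate and the separate report.
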